4.1 Inclusion criteria

1. Male or female ≥ 18 years at the time of screening.
2. Written informed consent and any locally required authorization (eg, Health Insurance Portability and Accountability Act in the US, EU Data Privacy Directive in the EU) obtained from the patient/legal representative prior to performing any protocol-related procedures, including screening evaluations.
3. Histologically or cytologically documented extensive disease American Joint Committee on Cancer Stage IV SCLC (T any, N any, M1 a/b) at initial diagnosis, also including patients with:
 - T3-4 due to multiple lung nodules that are too extensive or have tumor/nodal volume that is too large to be encompassed in a tolerable radiation plan.
 - Biopsy-proven mixed SCLC and NSCLC histology
 - Brain metastases; must be asymptomatic or treated and stable off steroids and anti-convulsants for at least 1 month prior to study treatment. Patients with suspected brain metastases at screening should have a computed tomography (CT)/magnetic resonance imaging (MRI) of the brain prior to study entry.
4. Patients must have demonstrated progressive disease (PD) either during first-line platinum-based chemotherapy (platinum refractory) or within 90 days of completing platinum-based chemotherapy (platinum resistant), and have not received further treatment apart from first-line platinum-based chemotherapy. Patients should be enrolled within 90 days of progression in order to be accepted into the study.
5. World Health Organization (WHO)/Eastern Cooperative Oncology Group (ECOG) Performance Status of 0 to 1 at enrollment for the first 10 patients recruited to this arm (see Section 6.3.1 of master protocol for WHO/ECOG assessment parameters). This can be extended to Performance Status 0 to 2 if the arm recruits an additional 10 patients.
6. At least 1 lesion, not previously irradiated, that can be accurately measured at baseline as ≥ 10 mm in the longest diameter (except lymph nodes, which must have a short axis ≥ 15 mm) with CT or MRI and that is suitable for accurate repeated measurements as per RECIST 1.1 guidelines.

7. No prior exposure to immune-mediated therapy including, but not limited to, other anti-CTLA-4, anti-PD-1, anti-PD-L1, and anti programmed cell death ligand 2 (anti-PD-L2) antibodies, excluding therapeutic anticancer vaccines.
8. Body weight >30 kg.

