 15. Radiation therapy to the chest and whole-brain irradiation must be completed at least 4 weeks prior to start of study treatment, and patients must have recovered from any acute adverse effects prior to start of study treatment. An exception to this is palliative radiotherapy for bone lesions and must be completed before the first dose of study treatment.
 16. Past medical history of interstitial lung disease, drug-induced pneumonitis, radiation pneumonitis that required steroid treatment, or any evidence of clinically active interstitial lung disease.
 17. History of hypersensitivity to active or inactive excipients of any investigational drug in the study or drugs with a similar chemical structure or class to those investigated in the study.
 18. History of another primary malignancy except for:
 - Malignancy treated with curative intent and with no known active disease ≥5 years before the first dose of study drug and of low potential risk for recurrence
 - Adequately treated non-melanoma skin cancer or lentigo maligna without evidence of disease
 - Adequately treated carcinoma in situ without evidence of disease (eg, cervical cancer in situ)
 19. History of leptomeningeal carcinomatosis.

20. History of active primary immunodeficiency.
21. History of allogenic organ transplantation.
22. Spinal cord compression unless asymptomatic or treated and stable off steroids and anti-convulsants for at least 1 month prior to study treatment.
23. Female patients who are pregnant or breastfeeding or male or female patients of reproductive potential who are not willing to employ effective birth control from screening to 90 days after the last dose of durvalumab monotherapy or 180 days after the last dose of durvalumab tremelimumab combination therapy.

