8.2.1 Duration of treatment and criteria for treatment through progression

All treatment will be administered beginning on Day 1 until confirmed PD unless there is unacceptable toxicity, withdrawal of consent, or another discontinuation criterion is met. Treatment through progression will only be considered for arms containing durvalumab +/- tremelimumab.

Progression during treatment

During the treatment period patients may continue receiving therapy in the setting of unconfirmed radiologic progressive disease (PD) according to Response Evaluation Criteria in Solid Tumors version 1.1 (RECIST 1.1), at the Investigator's discretion, until progression is confirmed. A confirmatory scan is required following a RECIST 1.1 overall time point assessment of progression (PD), preferably at the next scheduled visit and no earlier than 4

weeks after the previous assessment of PD. Patients with PD by RECIST 1.1 (unconfirmed and confirmed) who, in the Investigator's opinion, continue to receive benefit from their assigned treatment and who meet the criteria for treatment in the setting of PD may continue to receive their assigned treatment for as long as they are gaining clinical benefit. However, patients will not be permitted to continue immunotherapy if progression occurs after confirmed response (CR or PR as defined by RECIST 1.1) to immunotherapy treatment in the target lesions (regardless of the appearance of new lesions) i.e the response and progression events both occurred in the target lesions while receiving immunotherapy during the same treatment period.

Patients with rapid tumour progression or with symptomatic progression that requires urgent medical intervention (eg, central nervous system metastasis, respiratory failure due to tumor compression, spinal cord compression) will not be eligible for continuing durvalumab ± tremelimumab.

Patients in the durvalumab + tremelimumab combination therapy arm meeting the retreatment criteria below will follow the same treatment guidelines followed during the original treatment period, including the same dose and frequency of treatments and the same schedule of assessments (with the exception of the PK, ADA, tumor biopsies, biomarker samples and optional PGx assessments, which do not need to be collected a second time).

Patients who meet the criteria for retreatment may only receive retreatment once.

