Patients receiving the durvalumab + tremelimumab combination therapy arm may undergo retreatment as described below:

Patients who complete the 4 dosing cycles of the combination of durvalumab and tremelimumab portion of the regimen (with clinical benefit per Investigator judgment), but subsequently have evidence of PD during the durvalumab monotherapy portion of the combination regimen, with or without confirmation according to RECIST 1.1, may restart treatment with the combination.

For all patients who are treated through progression and for patients who are restarting durvalumab + tremelimumab the Investigator should ensure that:

- The patient does not have any significant, unacceptable, or irreversible toxicities that indicate continuing treatment will not further benefit the patient
- There is absence of clinical symptoms or signs indicating clinically significant disease progression accompanied by a decline in WHO/ECOG performance status to >1
- There is absence of rapid disease progression or threat to vital organs or critical anatomical sites (eg, central nervous system metastasis, respiratory failure due to tumor compression, or spinal cord compression) requiring urgent alternative medical intervention.

- The patient still fulfills the eligibility criteria for this study with the exception of inclusion criteria numbers 4 and 7, and exclusion criteria number 19.

During the retreatment period, patients in the durvalumab + tremelimumab combination therapy group will resume durvalumab dosing at 1500mg q4w with 75 mg of tremelimumab q4w for 4 doses/cycles each. Patients will then continue with durvalumab monotherapy at 1500mg q4w, beginning at Week 16, 4 weeks after the last dose of combination therapy until disease progression.

Patients who AstraZeneca and the Investigator determine may not continue treatment after PD will be followed up for survival. Patients who have discontinued treatment due to toxicity or symptomatic deterioration, or who have commenced subsequent anticancer therapy, will be followed up until confirmed disease progression and for survival.

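### Arm A's rule for treating through progression and retreatment waives exclusion 19, leptomeningeal carcinomatosis, which study treatment does not break, and gives no reason

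*Protocol*

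**What the plan says.** Protocol Appendix A section 8.2.1 sets conditions for two groups of Arm A patients: those who stay on treatment through progression, and those who restart the combination after progressing on durvalumab monotherapy. One condition is that they still meet the eligibility criteria "with the exception of inclusion criteria numbers 4 and 7, and exclusion criteria number 19".

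In the current Arm A lists (Appendix A sections 4.1 and 4.2):

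- Inclusion 4 requires progression on, or within 90 days of, first-line platinum, and that patients "have not received further treatment apart from first-line platinum-based chemotherapy". It also sets a 90-day limit from progression to enrolment.
- Inclusion 7 begins "No prior exposure to immune-mediated therapy including, but not limited to".
- Exclusion 19 is "History of leptomeningeal carcinomatosis".

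The neighbouring conditions in section 8.2.1 require no rapid progression and no threat to critical sites (central nervous system metastasis is one example, "or spinal cord compression) requiring urgent alternative medical intervention" closes the list). They also require no clinically significant progression "accompanied by a decline in WHO/ECOG performance status to >1". Earlier in the section, rapid progression or "symptomatic progression that requires urgent medical intervention" rules out continuing. A patient who restarts "will resume durvalumab dosing at 1500mg q4w with 75 mg of tremelimumab q4w for 4 doses/cycles each", then returns to durvalumab alone. Retreatment is allowed once.

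**The concern.** A waiver list in a retreatment rule normally holds criteria that the patient can no longer meet because of being on study. Two of the three items fit that description and the third does not. Prior leptomeningeal disease is an unqualified bar at entry in all three arms: Arm A exclusion 19, Arm B exclusion 20 and Arm C exclusion 10.

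No correctly enrolled patient has that history at entry, so the waiver can act only for someone who develops leptomeningeal disease during the study. For that patient it lifts the one Arm A criterion that names the condition. This is a rule sites use to decide on dosing. What is at stake is post-progression exposure to one or two checkpoint inhibitors, and safety, in a patient every arm would refuse at entry.

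**Working it through.** This is a cross-reference check. The only arithmetic is a count and one dose total.

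**1. Look up each waived number and ask whether study treatment breaks it.**

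| Waived item | Current content (Appendix A 4.1, 4.2) | Broken by study treatment? |
|---|---|---|
| Inclusion 4 | No therapy beyond first-line platinum; enrolled within 90 days of progression | Yes |
| Inclusion 7 | No earlier immune-mediated therapy | Yes |
| Exclusion 19 | Leptomeningeal carcinomatosis in the history | No |

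Waived: 3. Broken by treatment: 2. Remaining: 3 − 2 = 1.

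**2. Look for an exclusion that being on study does break.** Exclusion 2 bars anyone enrolled in this study before. Read literally, every patient on study meets it, and it is not waived. Exclusion 4 bars anyone randomized or treated in an earlier durvalumab or tremelimumab trial. Its wording points to other trials, but its subject is close to the purpose of the waiver. Either is a plausible intended target; neither can be established, because no earlier Arm A list is shown.

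**3. Is renumbering plausible?** The version history says the criteria were moved into the arm appendices. It also places the growth-factor restriction in Arm A inclusion 5, whereas it now stands in inclusion 12. The inclusion list was therefore renumbered at some point. This is background only: it says nothing direct about the exclusion list, and the mismatch lies wholly within current text.

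**4. What still stops a patient with new leptomeningeal disease?**

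- The central nervous system conditions in section 8.2.1 apply when progression is rapid or urgent intervention is needed.
- The performance-status condition needs a fall to above 1.
- Inclusion 3 stays in force but concerns brain metastases, which Appendix F section 2.2 lists separately from leptomeningeal disease.
- Exclusion 22 stays in force but concerns cord compression.
- The bar on continuing after response and then progression in target lesions is not triggered by leptomeningeal progression alone, because Appendix F section 2.2 classes such disease as non-measurable and so never a target lesion.
- The limit of 10 mg/day prednisone equivalent (exclusion 14), the 4-week interval after whole-brain irradiation (exclusion 15) and the 8-week life expectancy (inclusion 11) stay in force.
- Investigator judgement of benefit applies, and section 8.2.1 gives the sponsor a part in deciding who may not continue.
- Retreatment is open only to patients who completed four combination cycles with clinical benefit.

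None of these bars leptomeningeal disease as such. Together they leave a small gap: disease that is not urgent, has not brought performance status above 1, does not need excess steroid, and occurs in a patient judged to be benefiting and not stopped by the sponsor.

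**5. Exposure in one retreatment course.** Tremelimumab 4 × 75 mg = 300 mg; durvalumab 4 × 1500 mg = 6000 mg; then durvalumab 1500 mg every 4 weeks until progression. This describes the course the rule would permit. It does not measure harm.

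**The case against.** The strongest reply is that testing only whether study treatment breaks a criterion is too narrow. The rule covers patients whose disease has progressed, and a disease-status criterion can stop being met through progression. On that view the sponsor may have meant to leave such patients to the central nervous system conditions in the same list. This is coherent, and it stands to the extent that a deliberate waiver cannot be excluded. It does not remove the point: the protocol states no such reason, and lifting a named exclusion for post-progression checkpoint blockade should be stated and justified.

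A second reply is that several specific limits survive, including inclusion 3, exclusion 22 and sponsor involvement. That also stands, and it is why the affected case is narrow.

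A reader might infer more than the documents support. They do not prove a numbering error, since the intended criterion is not shown. They do not leave general safeguards and investigator judgement as the only protection, as step 4 shows. They do not admit patients with leptomeningeal disease at enrolment, where exclusion 19 applies in full.

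**Conclusion.** The point holds in this limited form. Section 8.2.1 waives a criterion that does not fit the evident purpose of the waiver, without explanation. The result is to remove Arm A's only explicit bar on leptomeningeal disease for patients who develop it on study and are considered for continued or repeat treatment. A wrong cross-reference is the likeliest explanation, though that is inference.

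Few patients would be affected. The documents give no incidence, so no number is offered. The primary ORR does not change, because master protocol section 9.4.1.2 uses data up to progression; sample size is also untouched. The matter is one of safety and clear instruction to sites. It is worth correcting because it governs dosing and the correction is small.

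The conclusion assumes that the Arm A numbering in the current text is the numbering section 8.2.1 refers to.

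**What to change.** In Appendix A section 8.2.1:

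- Keep exclusion 19 in force for treatment through progression and for retreatment, unless the sponsor's physicians state and justify a leptomeningeal exception.
- Name the waived criteria in words as well as by number, so that renumbering cannot alter the rule: inclusion 4 (no therapy beyond first-line platinum, enrolment window), inclusion 7 (no earlier immune-mediated therapy), and whichever exclusion was actually intended.
- In settling that, check exclusion 2, which read literally bars every retreated patient, and exclusion 4 on earlier durvalumab or tremelimumab trials. Deleting the reference to 19 without this check could lose a waiver the sponsor needs.

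The cost is one sentence in a protocol amendment, plus the sponsor's confirmation of what was meant. Sample size, assessments and analysis stay as they are.

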8.3 Labeling

Please refer to Section 8.3 of the master protocol for details regarding labeling applicable to all arms. Additional details regarding labeling applicable to Arm A are described below.

Label text prepared for durvalumab will show the product name as “MEDI4736” or “durvalumab (MEDI4736)” depending on the agreed product name used in the approved study master label document. All naming conventions are correct during this transitional period.

Label text prepared for tremelimumab will show the product name as “tremelimumab”.

8.4 Storage

Please see Section 8.4 of the master protocol.

8.5 Compliance

Please see Section 8.5 of the master protocol.

8.6 Accountability

Please see Section 8.6 of the master protocol.

8.7 Concomitant and other treatments

Please refer to Section 8.7 of the master protocol for details regarding concomitant and other treatments applicable to all arms. Details regarding concomitant and other treatments applicable to Arm A are described below.

Refer also to the Dosing Modification and Toxicity Management Guidelines in Appendix A Table 7.

Appendix A Table 7 Prohibited concomitant medications for Arm A

Prohibited medication/class of drug:	Usage
Any investigational anticancer therapy other than those under investigation in this study	Should not be given concomitantly
mAbs against CTLA-4, PD-1, or PD-L1	Should not be given concomitantly
Any concurrent chemotherapy, radiotherapy, immunotherapy, or biologic or hormonal therapy for cancer treatment other than those under investigation in this study	Should not be given during the study. (Concurrent use of hormones for non-cancer-related conditions [eg, insulin for diabetes and hormone replacement therapy] is acceptable. Local treatment of isolated lesions, excluding target lesions, for palliative intent is acceptable [eg, by local surgery or radiotherapy])
Immunosuppressive medications including, but not limited to, systemic corticosteroids at doses exceeding 10 mg/day of prednisone or equivalent, methotrexate, azathioprine, and TNF- α blockers	Should not be given concomitantly. (Use of immunosuppressive medications for the management of IP-related AEs or in patients with contrast allergies is acceptable). In addition, use of inhaled, topical, and intranasal corticosteroids is permitted.
Drugs with laxative properties and herbal or natural remedies for constipation	Should be used with caution through to 90 days after the last dose of tremelimumab during the study
Sunitinib	Should not be given concomitantly or through 90 days after the last dose of tremelimumab (acute renal failure has been reported with combination therapy of tremelimumab and sunitinib)
EGFR TKIs	Should not be given concomitantly Should be used with caution in the 90 days following the last dose of durvalumab Increased incidence of pneumonitis (with third generation EGFR TKIs) and increased incidence of transaminase increases (with first generation EGFR TKIs) have been reported when durvalumab has been given concomitantly.
Live attenuated vaccines	Should not be given through 30 days after the last dose of IP
Herbal and natural remedies which may have immune-modulating effects	Should not be given concomitantly unless agreed by the sponsor

AE Adverse event; CTLA-4 Cytotoxic T-lymphocyte-associated antigen 4; EGFR Epidermal growth factor receptor; IP Investigational product; mAb Monoclonal antibody; PD-1 Programmed cell death 1; PD-L1 Programmed cell death ligand 1; TKI tyrosine kinase inhibitor; TNF Tumor necrosis factor.

Appendix A Table 8 Rescue/supportive medication for Arm A

Rescue/supportive medication	Usage
Concomitant medications or treatments (eg, acetaminophen or diphenhydramine) deemed necessary to provide adequate prophylactic or supportive care, except for those medications identified as “prohibited,” as listed above	To be administered as prescribed by the Investigator
Best supportive care (including antibiotics, nutritional support, correction of metabolic disorders, optimal symptom control, and pain management [including palliative radiotherapy to non-target lesions, etc])	Should be used, when necessary, for all patients
Inactivated viruses, such as those in the influenza vaccine	Permitted

8.8 Post Study Access to Study Treatment

Please see Section 8.8 of the master protocol.

9. STATISTICAL ANALYSES BY ASTRAZENECA

Please refer to Section 9 of the master protocol for details regarding statistical analyses applicable to all arms. Additional details regarding statistical analyses applicable to Arm A are described below.

CCI

CCI

9.2 Adverse events

AEs observed up to 90 days following discontinuation of study treatment or until the initiation of the first subsequent therapy following discontinuation of treatment (whichever occurs first) will be used for the reporting of AE summary tables. This will more accurately depict AEs attributable to study treatment only, as a number of AEs up to 90 days following discontinuation of the study agents are likely to be attributable to subsequent therapy.

9.3 Study and data management by AstraZeneca

Please refer to Section [10](#) of the master protocol for details of the management of the study and data.

10. ETHICAL AND REGULATORY REQUIREMENTS

Please refer to Section [11](#) of the master protocol for details regarding ethical and regulatory requirements.

APPENDIX B ARM B: AZD1775 + CARBOPLATIN SUB-PROTOCOL

1. LIST OF ABBREVIATIONS AND DEFINITION OF TERMS

The following abbreviations and special terms are used in this study Clinical Study Protocol.

Abbreviation or special term	Explanation
AE	Adverse event
ALT	Alanine aminotransferase
ANC	Absolute neutrophil count
AST	Aspartate aminotransferase
AUC	Area under the plasma drug concentration-time curve
AUC(0-∞)	Area under the plasma drug concentration-time curve time 0 to infinity
BCRP	Breast cancer resistance protein
BID	Twice daily
CBDP	Carboplatin
CIDP	Chronic inflammatory demyelinating polyneuropathy
C _{max,ss}	Maximum plasma concentration at steady state
CrCl	Creatinine clearance
CRF	Case report form (electronic/paper)
CTCAE	Common Terminology Criteria for Adverse Event
CYP	Cytochrome P450
DHEA	Dehydroepiandrosterone
DNA	Deoxyribonucleic acid
DLT	Dose-limiting toxicity
ECG	Electrocardiogram
eCRF	Electronic case report form
ECOG	Eastern Cooperative Oncology Group
ED-SCLC	Extensive stage disease small-cell lung cancer

Abbreviation or special term	Explanation
5-FU	5-fluorouracil
FDA	Food and Drug Administration
GFR	Glomerular filtration rate
IB	Investigator's Brochure
IRB	Institutional Review Board
IP	Investigational product
IV	Intravenous
MATE	Multi-antimicrobial extrusion protein
MTD	Maximum tolerated dose
NCI	National Cancer Institute
NSCLC	Non-small cell lung cancer
ORR	Objective response rate
OS	Overall survival
p53	Tumor protein 53
P-gp	P glycoprotein
PD	Progressive disease
PFS	Progression-free survival
PO	By mouth
PK	Pharmacokinetic(s)
PR	Partial response
q3w	Every 3 weeks
q4w	Every 4 weeks
q6w	Every 6 weeks
q12w	Every 12 weeks
RECIST 1.1	Response Evaluation Criteria in Solid Tumors
SAE	Serious adverse event
SD	Stable disease
SCLC	small cell lung cancer
ULN	Upper limit of normal

Abbreviation or special term	Explanation
WEE1	A nuclear kinase belonging to the Ser/Thr family of protein kinases in the fission yeast Schizosaccharomyces pombe (S. pombe).
WoCBP	Women of childbearing potential

